## 10. DATA ANALYSIS

### 10.1. Data Quality Assurance

To maintain accuracy, consistency and completeness of data, periodic audits and self-assessments will be conducted. The data will be cross-checked by the study coordinator and the PIs to maintain quality control.

### 10.2. Data Entry and Storage

All data will be entered and stored into a Redcap project drive to ensure maximal security and anonymity.

## 11. SAMPLE SIZE AND STATISTICAL METHODS

### 11.1. Determination of Sample Size

Thirty (n=30) subjects recruited from Texas will be sought for each group for a total enrollment of sixty (n=60). This is from a power analysis performed. The minimal clinically significant difference in visual acuity score (0-10) is 2 points, or 20%, as established in a prior study. In order to ensure 80% power at an alpha of 0.05, 26 patients are needed in each study group. Minimal attrition is expected given that there is no routine follow-up necessary.

### 11.2. Statistical and Analytical Plans

Demographic variables and diagnostic outcomes will be compared using t-test for continuous variables and chi-square or Fisher exact test for categorical variables. A Mann-Whitney rank sum test will be used to compare median visual clarity scores. In the case where a serious medication-related adverse events occurs, we will also start an early analysis to determine the potential causes.

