#### **2.3. Secondary Objectives**

To evaluate mean arterial pressure, operative time, and any adverse events that occur during arthroscopic shoulder surgery.

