#### **3.2. Criteria for Recruitment**

Our study population will be adult (18 years of age or older) patients undergoing arthroscopic shoulder surgery requiring visualization within the subacromial space. This includes primarily arthroscopic rotator cuff debridement or repair, arthroscopic subacromial decompression, arthroscopic subacromial bursectomy or bursal debridement, and arthroscopic distal clavicle resection, among other arthroscopic procedures. Only procedures performed in the seated, upright (ie, beach chair) position will be included. Study participation will be contingent upon signed informed consent obtained prior to performing data collection or study procedures.

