#### UTHealth CTRC DSMP Checklist

- Primary and secondary outcome measures
  - o Primary: surgeon-rated visual clarity score (visual analog scale 0 to 10), changes in intra-operative arthroscopic pump pressure
  - o Secondary: mean arterial pressure intra-operatively, total operative time, adverse events intra-operatively or post-operatively
  - o Inclusion: patients 18 years of age or older who are able to provide informed consent and who are to undergo arthroscopic shoulder surgery in the seated upright (beach-chair) position requiring visualization of within the subacromial space.
  - o Exclusion: Are unable to provide informed consent, non-English speaker, have a history of adverse medication reaction to epinephrine, and who are having arthroscopic shoulder surgery that does not require visualization within the subacromial space or performed in the lateral position.
  - o Sample size: Thirty (n=30) subjects recruited from Texas will be sought for each group for a total enrollment of sixty (n=60). This is from a power analysis performed. The minimal clinically significant difference in visual acuity score (0-10) is 2 points, or 20%, as established in a prior study. In order to ensure 80% power at an alpha of 0.05, a minimum of 26 patients are needed in each study group.
- List of participating enrolling clinics or data collection centers
  - o Memorial Hermann Memorial City Medical Center
  - o Memorial Hermann Surgery Center West Houston
  - o Memorial Hermann Orthopedic & Spine Hospital
  - o Memorial Hermann Surgery Center
  - o UT Physicians Orthopedics – Texas Medical Center
  - o UT Physicians Orthopedics – Memorial City
- Projected timeline
  - o Based on historic clinic data for the principal investigator and co-investigators, we anticipate meeting our enrollment target around 12 weeks from opening enrollment. Once enrolled, subjects will be randomized into either the epinephrine or placebo group. Surgeon-rated visual clarity score will be obtained immediately post-operatively.
- Target population distribution (e.g., women, minorities, etc.)
  - o The target population distribution will be the typical patients that the principal investigator and co-investigators schedules and operates on here at the UT Health and Memorial Hermann Health systems. Randomization will ensure that both groups will have similar demographic backgrounds.
- Data acquisition and transmission

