  - o Clinical assessments and images will be uploaded and stored on Epic and Centricity as is standard. The recorded assessments and images will be stored for study use for at least six years, with all study related data stored in Redcap.
  - o Demographic data (name, age, gender, weight, race) will be collected from medical records and stored in Redcap.
  - o Surgical data (start and stop times for procedure, type of procedure performed, mean arterial pressure) will be recorded and stored in Redcap.

- Objective clinical data (adverse events) will be collected during the post-operative period with information collected stored in Redcap.
  - Subjective clinical data (surgeon-rated visual clarity score, surgeon-requested increase in arthroscopic irrigation pump pressure) will be recorded and stored in Redcap.
  - Imaging data (none)
- Data entry methods
  - A linking log and data collection form will be used to protect subjects' PHI. All data will be entered and stored in a Redcap project drive to ensure maximal security and anonymity.
- Data analysis plan
  - Demographic variables and diagnostic outcomes will be compared using t-test for continuous variables and chi-square or Fisher exact test for categorical variables. A Mann-Whitney rank sum test will be used to compare median visual clarity scores.
- Quality assurance plan
  - To maintain accuracy, consistency and completeness of data, periodic audits and self-assessments will be conducted. The data will be cross-checked by the study coordinator and the PIs to maintain quality control.
- Reporting mechanisms of AEs/SAEs to the IRB, FDA, and NIDA
  - The principal investigator will report all AEs and SAEs occurring in clinical investigations to the IRB according to the UTHSC-Houston IRB policy. A definition of what constitutes an AE or SAE can be found below in this document as well as within the study protocol.
    - AEs will be compiled and submitted on an annual basis to the IRB. Each AE will require review from the investigator as soon as identified.
    - SAEs will be reviewed by the investigator as soon as identified, and all SAEs will be reported to the IRB within 48 hours of identification.
- Reporting mechanisms of IRB actions to NIDA
  - No drugs are involved in this study, so reporting to the NIDA will not be necessary.
- Report of changes or amendments to the protocol

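### Operative time and mean arterial pressure have only a generic unadjusted t-test as their default analysis, which gives up precision that procedure type and a pre-injection pressure reading could recover

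*Combined protocol and SAP*

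**What the plan says.** Section 2.3 sets the secondary objective: "To evaluate mean arterial pressure, operative time, and any adverse events that occur during arthroscopic shoulder surgery". The DSMP checklist in Section 9.3 repeats it as an outcome list: "Secondary: mean arterial pressure intra-operatively, total operative time, adverse events intra-operatively or post-operatively".

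The analysis rule in Section 11.2, repeated in the checklist, reads: "Demographic variables and diagnostic outcomes will be compared using t-test for continuous variables"; categorical data go to a chi-square or Fisher test. The next sentence deals with visual clarity alone: "A Mann-Whitney rank sum test will be used to compare median visual clarity scores". No regression, ANCOVA or stratified analysis appears anywhere in the document.

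Three other parts of the plan bear on the choice of analysis:

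- **Case mix.** Section 3.2 admits a range of operations, including "arthroscopic rotator cuff debridement or repair, arthroscopic subacromial decompression", bursectomy, distal clavicle resection and others.
- **Randomization.** Section 6.1 specifies simple randomization, with no stratification by procedure.
- **Data recorded.** The checklist states: "Surgical data (start and stop times for procedure, type of procedure performed, mean arterial pressure) will be recorded and stored in Redcap". Section 5.1 adds that MAP is monitored during the case. No pre-injection reading is listed as a data item, and no summary of the MAP series is defined.

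**The concern.** When operations of different expected length are pooled and raw times are compared, the variation between procedures goes into the error term. If procedure type explains much of the variance, the trial discards information that it already collects. The same holds for MAP if a reading from before the injection predicts later readings.

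Shorter operating time is one of the benefits claimed for the epinephrine injection (Sections 2.4 and 9.3), so a wide interval on that outcome weakens what the trial can say about it. Section 1.2.d promises to collect potential confounders, with visual clarity in mind, but no analysis uses them for any outcome.

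**Working it through.** **The plan's own figure.** The only sample-size figure is 26 per group for visual clarity (2 points, 80% power, alpha 0.05; Section 11.1). No SD is given, so it cannot be reproduced. Solving backwards for a two-sided t-test gives an SD of about 2.5. The figure does not concern operative time or MAP, for which the plan states no target difference, SD or power.

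**Inputs.** From the documents: 30 per arm. Assumed: two-sided alpha 0.05, equal arms, 60% repairs, a true 15% reduction in operative time, lognormal times, and the medians and within-procedure CVs shown below.

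**Operative time, formulas on the log scale**

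- Effect: δ = −ln(0.85) = 0.1625.
- Within-procedure variance: ln(1 + CV²).
- Between-procedure variance: 0.6 × 0.4 × [ln(median ratio)]².
- Standardized effect: δ/SD, with the total SD if unadjusted and the within-procedure SD if adjusted.
- Power: noncentral t with noncentrality (δ/SD) × √(30/2).

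| Medians, repair / other (min) | CV | Within SD | Total SD | R² of procedure | δ/SD unadjusted | δ/SD adjusted | Power unadjusted | Power adjusted |
|---|---|---|---|---|---|---|---|---|
| 90 / 45 | 25% | 0.246 | 0.419 | 0.66 | 0.387 | 0.660 | 31% | 71% |
| 80 / 55 | 35% | 0.340 | 0.386 | 0.23 | 0.421 | 0.478 | 36% | 44% |
| 90 / 70 | 35% | 0.340 | 0.362 | 0.12 | 0.450 | 0.478 | 40% | 44% |

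Simulated trials that set the t-test on raw minutes against the log model with procedure agree: about 31% to 70%, 36% to 45%, and 38% to 43%. Repeat runs differ by one or two points. The last two scenarios share one CV, so their adjusted power is the same (44% by formula), and the 45% and 43% differ only by simulation error. A t-test on log minutes without procedure has about the same power as one on raw minutes, so the gain comes from the covariate and not from the log.

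**MAP.** Assumed: 5 mmHg difference, SD 10, so d = 0.5. Adjusting for a baseline with correlation r leaves a residual SD of 10 × √(1 − r²).

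| r | Residual SD | Power | Interval narrower by |
|---|---|---|---|
| none | 10.0 | 48% | – |
| 0.3 | 9.5 | 51% | 5% |
| 0.5 | 8.7 | 59% | 13% |
| 0.6 | 8.0 | 66% | 20% |

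**General scale.** Adjustment acts like raising n per arm from 30 to 30/(1 − R²): 33 at R² = 0.1, 37.5 at 0.2, 43 at 0.3 and 60 at 0.5.

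**Validity.** With no treatment effect, the unadjusted t-test rejected in about 4% to 5% of simulated trials. It holds its nominal error rate despite the mixed procedures and simple randomization.

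**The case against.** The strongest reply is that these are secondary outcomes with no power claim, that the planned test is valid, and that the gain may be slight. All of this stands. With medians of 90 and 70 minutes, adjustment adds about five points and the comparison stays below 50% power. At a MAP correlation of 0.3 it adds three. The visual clarity comparison and the sample size are untouched.

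Several stronger readings are tempting, but the documents do not support them:

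- **That the plan assigns the t-test to these two outcomes.** Section 11.2 speaks of demographic variables and diagnostic outcomes. Applying it to operative time and MAP is the default reading, because nothing else in the plan would cover them. If it does not apply, they have no stated analysis.
- **That the t-test would report a chance imbalance in repairs as a treatment effect.** Such imbalance is already counted in the test's error rate, as the simulation under no effect shows.
- **That much of the power is certainly lost.** The large gain needs repairs to take twice as long and a CV of only 25%. The documents give no operative times, SDs or correlations.
- **That a pre-injection MAP is already in hand, so only wording need change.** Monitoring during the case is not the same as a recorded baseline value. Likewise, the checklist records the procedure performed, not the procedure planned.

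**Conclusion.** The point holds as one of precision and prespecification. The only analysis on offer for operative time and MAP is an unadjusted t-test, reached by default, while a likely predictor of operative time is collected and left unused. The test is valid, so neither bias nor false positives are at issue.

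The size of the loss is unknown. Across the assumed scenarios, adjustment adds between about 5 and 39 power points for operative time, and between 3 and 18 for MAP. The upper ends rest on a wide gap between procedures with a small CV, and on a baseline correlation of 0.6. This is a worthwhile, low-cost improvement to secondary analyses and does not threaten the trial's main comparison.

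**What to change.** In Section 11.2 and in the matching checklist entry, name the analysis for each outcome:

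- **Operative time:** a linear model on log minutes with terms for arm and procedure type (repair or no repair). Report the ratio of times with its 95% confidence interval. Preferably use the procedure planned before the injection, because the procedure performed is known only afterwards.
- **MAP:** define the outcome as mean MAP from injection to the end of the case. Where a pre-injection reading is captured, analyse by ANCOVA with arm and that reading.

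The cost is small but goes beyond wording: the planned procedure and one pre-injection MAP value must be added as data items. The operative-time result becomes a ratio rather than a difference in minutes; unadjusted times by arm can be shown beside it for readers who want minutes. No extra patients or visits are needed.

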## 12. ETHICAL CONSIDERATIONS

### 12.1. Informed Consent

This study will obtain written informed consent prior to performing any study-related data collection. Research coordinators will obtain informed consent from the patient prior to administration of sedation. Consent will be obtained under the direction of [name]. In obtaining and documenting informed consent, we will ensure compliance with all GCP guidelines and standard ethical principles.

## **12.2. IRB review**

This protocol and the associated informed consent documents will be submitted to the IRB for review and approval.

## **12.3. Confidentiality of Data and Patient Records**

All study-related data will be de-identified and stored on a password-protected server within the Department of Orthopaedic Surgery, accessible only by study-specific personnel identified in this protocol. Records will be maintained for at least six years after study completion as per University Policy. Protected health information (PHI) will not be disclosed to any third party and will not be published in any research reports that result from their inclusion in the study.

## **13. PUBLICATIONS**

We plan to publish the results of this study in the form of posters/abstracts for orthopedic-related organization meetings and manuscripts to orthopedic journals; however, no identify or personal information regarding the subjects will be reported. The results of this study will be submitted for publication and for coverage by scientific media. Dissemination to policy makers within the orthopedic community will be considered as well, pending results. Results will be returned to the research subjects upon request.

## **14. RETENTION OF TRIAL DOCUMENTS**

Records for all participants and study-related documentation (consisting of evidence to study eligibility, history and physical findings, clinical data) as well as IRB records and other regulatory documentation will be retained by the PI in a secure fashion. These records will be made available for inspection and copying by authorized authorities upon request.
